#### 4.5. Schedule of Assessment (in Diagrammatic Format)

Figure 6 describes the time points at which assessments and data will be collected.

Measure	Researcher or participant completing	At assessment (T0)	Every two weeks of Prehab	On Prehab Completion (T1)	At hospital discharge (T2)	1 month post-op (T3)	3 month post-op (T4)	1 year post-op (T5)
EORTC QLQ-C30	Participant	+	-	+	+	+	+	-
Dyspnoea score	Researcher	+	+	+	+	+	-	-
PS	Researcher	+	+	+	+	+	-	-
Thoracoscore	Researcher	+		+	-	-	-	-
Frailty index	Researcher	+	+	+	+	+	-	-
LOA	Researcher	+	+	+	+	+	-	-
Researcher	Researcher	+	+	+	+	+	-	-
MIP	Researcher	+	-	+	+	-	-	-
FEV1	Researcher	+	-	-	-	-	-	-
TLCO	Researcher	+	-	-	-	-	-	-
HLOS (days)	Researcher	-	-	-	+	-	-	-
Mortality	Researcher	-	-	-	+	+	+	+
Post-op complications	Researcher	-	-	-	+	-	-	-

**Figure 6. Time points at which assessments will be carried out and data collected.**

6MWD test= 6 minute walk test; EORTC = European Organization for Research and Treatment of Cancer; FEV1= Forced expiratory volume in 1 second; MIP = Maximum inspiratory pressure; IMT= Inspiratory muscle training pressure; LOA = level of activity; HLOS = Hospital length of stay; PS= performance status; TLCO= transfer factor; QLQ-C30 = quality of life questionnaire.

#### 4.6. Follow up Procedures (if applicable)

Outcome measures (as highlighted in the above diagram) will be assessed using the European Organisation for Research and Treatment of Cancer (EORTC) quality of life (QoL) questionnaire, the EORTC QLQ-30 (9).

- commencement of Prehab (T0).
- every two weeks of Prehab
- On Prehab completion (prior to surgery) (T1).
- following surgery at the time of discharge from hospital (T2).
- one-month post-surgery (T3).
- 3 months post-surgery (T4).
- 12-month post-surgery (T5).

Outcome measures will be assessed via the telephone or face to face in the cardiothoracic physiotherapy department at Morriston Hospital, or the satellite center by the CI or research team.

#### **4.7. Laboratory Assessments (not applicable)**

#### **4.8. Radiology Assessments (not applicable)**

#### **4.9. End of Study Definition**

The parameters that will mark the end of the study will be the recruitment of 100 patients with a 12 month follow up period.

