**STUDY SUMMARY/SYNOPSIS**

TITLE	A randomised controlled trial to evaluate the impact of thoracic PRehabilitation with Inspiratory Muscle tRaining cOmpared to Standard prEhabilitation in surgical lung cancer patients.
SHORT TITLE	PRIMROSE Trial
Protocol Version Number and Date	Standard Protocol Version Number 3.5 and date 03/02/25
Methodology	Type of study: randomised control trial
Study Duration	Two years
Study Centre	Cardiothoracic centre, Morriston Hospital
Objectives	To compare inspiratory muscle training (IMT) with standard Prehabilitation (Prehab) to Prehab alone, in lung cancer patients for surgery.
Number of Subjects/Patients	One hundred and thirty-four patients will be recruited for the study (67 for each arm) and with an anticipated attrition rate of 20-25%, one hundred patients will finally be studied.
Main Inclusion Criteria	
All adult lung cancer patients > 18 years diagnosed or suspected of non-small cell lung cancer (NSCLC) with surgically resectable disease, who are referred for pre-treatment optimization with Prehab from the lung cancer Multi-Disciplinary Teams (MDTs) across South West Wales (Swansea lung MDTs, the Hywel Dda lung MDTs and Princess of Wales lung MDT).
 
Lung cancer patient are referred for pre-treatment optimization with Prehab if they meet the following referral criteria: <math>\geq 1</math> Medical Research Council (MRC) dyspnoea score; or <math>\geq 1</math> World Health Organization (WHO)

	
performance status (PS); age <math>\geq 70</math> years or frailty index <math>>3</math>; borderline or poor pulmonary function (forced expiratory volume in one second (FEV1) or diffusion capacity for carbon monoxide (DLCO) <math><50\%</math>); sedentary patients despite having adequate FEV1 or DLCO. Patients will be included in the trial if they are capable of giving consent to participation and aged 18 and over.
 
Additionally, patients who have no contraindications to IMT use.

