## 1. Introduction

### 1.1. Background

Lung cancer is the most common cause of cancer-related deaths in Wales (1). Although surgical resection for early-stage lung cancer with curative intent remains the primary treatment, patients with significant smoking related underlying cardiopulmonary disease and impaired pulmonary function, dyspnoea, frailty and decreased activity levels are unfit for surgery and referred for alternative treatment (2,3). Secondly, individuals who proceed to lung resection, thoracic surgery and general anaesthesia may have direct effects on their respiratory system potentially leading to postoperative pulmonary complications (PPCs), which increases hospital morbidity, prolongs hospital length of stay (HLOS) impacts on the quality of life (QOL) of patients and adds to health-care costs (4). Our aim is to evaluate whether incorporating a breathing training device, POWERBreathe into the existing standardised thoracic prehabilitation program (Prehab) will optimise unfit patients physically for surgery, and following surgery reduce their risk of developing PPC's, reduce HLOS and improve QOL of patients and improve service outcomes (5).

The PRIMROSE study aims to compare two groups of patients referred for Prehab who have lung cancer treatable with surgery: (A) standard Prehab and training with the inspiratory muscle training (IMT) device; and (B) standard Prehab alone, in non-small cell lung cancer patients (NSCLC) undergoing lung resection surgery, with clear primary and secondary outcome measures.

One hundred and thirty-four patients will be recruited for the study (67 for each arm) and with an anticipated attrition rate of 25%, one hundred patients will finally be studied (6,7). With 134 recruited and an attrition rate of 25%, only 100 will remain (50 in each arm). The primary outcome measure tested will be the proportion of patients in each group experiencing postoperative pulmonary complications (PPC), which will be graded I-V using the Clavien Dindo Classification (8). PPCs will be broadly classified as minor (grade 1) and major complications (grade 2-5 where 5 is death). What we want to learn from this RCT study is whether IMT helps reduce grade  $\geq 2$  PPCs to either grade 1 or no complications and thereby help shorten the length of stay in hospital for patients undergoing lung resection surgery.

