## 2. Objectives and Design

### 2.1. Trial Objectives

**Primary Objective:** A randomised controlled trial to evaluate the impact of thoracic PRehabilitation with Inspiratory Muscle tRaining cOmpared to Standard prEhabilitation in surgical lung cancer patients [PRIMROSE Trial].

**Recruitment rate:** The study aims to recruit 134 patients for randomisation over twelve months, with 67 randomised to the intervention group and 67 to the control group (6).

**Retention rate:** These are high-risk patients and a high attrition rate in this population is considered normal. We anticipate the retention of 50 patients in each arm following 1:1 randomisation, and is based on our previous study (15), which showed that following assessment, 6.8% NSCLC patients fail to attend Prehab and 1.1% died prior to commencing Prehab. Likewise, following Prehab, 75.8% patients are ready to proceed with surgery. The attrition rate is an estimate and is anticipated attrition to be 20%-25%.

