**Figure 5: Online calculator to estimate sample size (29).**

This sample size is realistic as Prehab receives on an average of 127 annual patient referrals per year.

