#### **2.4.2 Analysis Plan**

Our aim is to evaluate the impact of thoracic Prehab with IMT compared to standard Prehab in reducing post operative pulmonary complications following surgical resection in lung cancer patients in a RCT.

The analysis will include descriptive data (means and standard deviation) on all outcomes collected, including levels of missing data, leading to the calculation of clinically important differences. Descriptive statistics will be used to summarise participants' baseline characteristics and outcome measures.

Statistical analyses will be performed using SPSS statistical software, version 20.0 (IBM Corporation, Armonk, NY, USA). Two-sided significance tests will be used ( $\alpha \leq 0.05$ ). Data will be presented as mean and standard deviation (SD), or median and interquartile range (IQR) for variables with a skewed distribution. Differences between groups in categorical variables will be tested with Chi square or Fisher's exact test. For continuous data the student's t test or the Mann-Whitney U test will be used. The Wilcoxon signed rank test will be used to compare MIP and QoL at T0 and T1 and T3. Relative risk will be calculated for post operative pulmonary complications (PPCs) graded 1-V using the Clavien Dindo classification and impact of IMT on the study group compared to the control group. Assuming a 36.7% incidence of PPC after surgery in the control arm and using a significance level of 0.05 and a power of 80%, 50 patients are required in each arm of the study for analysis."

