### 3. Subject Selection

#### 3.1. Number of subjects and subject Selection

Daily screening of new prehab referrals by the principal investigator or research team, using a consecutive sample approach will be used for participant recruitment. This means selecting all patients who meet the eligibility criteria. Patients over a 12-month period (from January 2025) will be approached to gain consent. However, if recruitment numbers are an issue the study will be extended by six months.

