## 4.4. Schedule of Treatment for each visit

On initial face-to-face assessment, conducted within 5 working days of receiving the referral for Prehab, the research team will provide participants with participant information sheet and informed consent form. Informed consent to participate will be obtained. Patients can bring carers to the face-to face assessment if they wish.

**Control group:** The control group will receive a standard Prehab protocol.

**Standard Prehab protocol** is described in our previous pragmatic study published in the Lancet journal *Journal of Clinical Medicine* (15). Prehab will be provided to participants over 2–4 weeks with supervised once weekly sessions ~~with supervised two weekly sessions~~ of 70 minutes each, along with exercises for patients to carry out at home. Three weeks is an anticipated average based on published data and urgency to proceed to surgery as cancer can grow and become inoperable by six weeks. This area is much debated in the Prehab literature. Our aim is to ensure as many patients benefit with Prehab followed by lung resection surgery as possible, with broader health benefits to patients and a positive impact on their quality of life. Our previous study showed that patients can be physically optimised safely in as little as two weeks (15). However, for patients who may be slower to respond there is scope in our program for a more prolonged course of Prehab if required.

Outcome measures will be collected every two weeks on the Prehab programme by the research team, which is standard practice. As patients become eligible, they will withdraw from Prehab and proceed to surgery once a surgical date is confirmed. Management of individuals deemed unfit for surgery will be discussed at the individuals' local lung cancer MDT for consideration of alternative treatment options namely, radiotherapy, systemic anti-cancer treatment or palliative care.

**Respiratory muscle training and breathing exercises.** Both groups will receive incentive spirometry devices pre operatively. Participants will be encouraged to practice and train with the spirometer device three times daily, so can use the spirometer effectively post operatively. This is standard care as spirometers aid lung volumes and removal of secretions post operatively.

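### Section 4.9 ends the study on 100 patients recruited, but everywhere else the protocol recruits 134 so that 100 remain for analysis

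*Protocol*

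**What the plan says.** Section 4.9 (End of Study Definition) consists of one sentence: the parameters that close the study "will be the recruitment of 100 patients with a 12 month follow up period".

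The rest of the protocol uses the numbers differently:

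- The synopsis recruits 134 patients, 67 per arm, and adds that "with an anticipated attrition rate of 20-25%, one hundred patients will finally be studied".
- Section 1.1 links the two figures: "With 134 recruited and an attrition rate of 25%, only 100 will remain (50 in each arm".
- Section 2.1 says: "The study aims to recruit 134 patients for randomisation over twelve months". It puts anticipated attrition at 20-25% and expects 50 patients retained per arm.
- Section 2.4.2 says that "50 patients are required in each arm of the study for analysis".

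Section 4.6 counts the 12-month visit (T5) from surgery. Appendix 1 expects the protocol to define the end of the trial, and sets an end-of-study declaration within 90 days of conclusion or 15 days of early termination.

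**The concern.** Outside section 4.9, 134 is the number recruited and 100 is the number left. Section 4.9 attaches the verb for the first to the figure for the second. That sentence fixes when the trial is over and starts the clock for the declaration in Appendix 1, so the wrong quantity there matters more than it would in background text.

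If the study team took the sentence at face value and closed recruitment at 100, the allowance for attrition would disappear and the primary analysis would fall short of the 50 per arm on which the stated 80% power depends. If nobody acted on it, the trial would still lack a clear rule for when it has ended.

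**Working it through.** **1. Reproduce the plan's own figure.** Inputs: 100 needed for analysis (50 per arm, section 2.4.2); attrition 25% (section 1.1).

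- Total: N = 100/(1 - 0.25) = 133.3, rounded up to 134.
- Per arm: 50/(1 - 0.25) = 66.7, rounded up to 67.
- Check: 134 × 0.75 = 100.5, about 100.

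The protocol's 134 (67 per arm) is reproduced exactly. So 134 is the recruitment figure and 100 the post-attrition figure, and the sample-size arithmetic itself contains no error.

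**2. Apply section 4.9 literally.** Inputs: 100 recruited (section 4.9); attrition 20-25% (synopsis, section 2.1).

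- At 25%: 100 × 0.75 = 75, i.e. 37 + 38.
- At 20%: 100 × 0.80 = 80, i.e. 40 + 40.

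This is 20-25 patients, or 20-25%, below the required 100. The step uses only figures in the protocol.

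**3. Illustrate the effect on power.** Inputs: control-arm rate of postoperative pulmonary complications 36.7%, significance level 0.05, power 80% (section 2.4.1); two-sided tests (section 2.4.2); 1:1 allocation (section 4.3). The readable text gives no intervention-arm rate, because Figure 5 is not shown. Assumption: the rate is the one that gives 80% power at 50 per arm.

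Unpooled normal approximation: power = Φ(d/SE - 1.96), where d = p1 - p2 and SE = √[p1(1 - p1)/n1 + p2(1 - p2)/n2]. Solving for 80% at n1 = n2 = 50 with p1 = 0.367 gives p2 = 0.1333. The pooled-variance formula gives p2 = 0.1280.

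With p2 = 0.1333, d = 0.2337, p1(1 - p1) = 0.2323 and p2(1 - p2) = 0.1155:

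- 50 + 50: SE = 0.0834, d/SE = 2.802, power = Φ(0.842) = 0.80.
- 40 + 40: SE = 0.0933, d/SE = 2.506, power = Φ(0.546) = 0.71.
- 37 + 38: SE = 0.0965, d/SE = 2.421, power = Φ(0.461) = 0.68.

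| Analysed | Unpooled (p2 = 0.1333) | Pooled (p2 = 0.1280) | Exact power of the uncorrected chi-square test (at 0.1333 / 0.1280) |
|---|---|---|---|
| 50 + 50 | 0.800 | 0.800 | 0.791 / 0.813 |
| 40 + 40 | 0.707 | 0.705 | 0.694 / 0.718 |
| 37 + 38 | 0.678 | 0.677 | 0.666 / 0.691 |

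The methods agree to within about two percentage points: roughly 68% at 25% attrition and 71% at 20%.

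**The case against.** The strongest reply is that section 4.9 is only loosely worded. It defines the end of the study and does not say that enrolment stops at 100. The target of 134 is stated in three other places. The 12 months are counted from surgery, and section 3.4 withdraws patients no longer suitable for resection, so patients with 12 months of follow-up are already a post-attrition group. On that reading 100 matches the number finally studied in the synopsis, and only the word for recruitment is wrong. This is plausible, and it is why the point is minor. It does not remove the contradiction: the protocol uses that word for 134 everywhere else, and this is the sentence that has to be exact.

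The intention-to-treat statement in section 4.12 does not settle the matter. The 134 allows for patients who never reach surgery (section 2.1 reports 75.8% ready after Prehab), and the primary outcome is assessed after surgery, up to discharge.

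It is also fair to object that the power figures depend on a back-solved rate. They do, and they only illustrate the shortfall of 20-25 patients, which needs no assumption.

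A reader might go further and infer either of two things that the documents do not support:

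- **That 134 cannot be recruited.** Section 2.4.1 says "This sample size is realistic as Prehab receives on an average of 127 annual patient referrals per year", and 134 exceeds 127. But that sentence follows the estimate of 50 per arm and may refer to 100. Section 2.1 states an aim, and section 3.1 provides that "if recruitment numbers are an issue the study will be extended by six months". Over 18 months, 127 × 1.5 = 190.5 referrals, of which 134 is about 70%. The pace is a separate feasibility question and is not evidence about section 4.9.
- **That the two-year duration in the synopsis is wrong.** Section 4.4 says "Prehab will be provided to participants over 2–4 weeks". Twelve months of recruitment, that Prehab period and 12 months of follow-up come to about 24.5-24.9 months. That is rounding.

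**Conclusion.** The inconsistency is real and can be seen from the protocol alone: section 4.9 gives 100 as recruited, where the synopsis, section 1.1 and section 2.1 give 134, and where sections 1.1 and 2.4.2 make 100 the number for analysis. It is a misplaced sample-size figure, of minor severity.

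Its effect depends on how the sentence is used. Taken literally, it means 75-80 patients analysed and power of roughly 68-71% instead of 80%, conditional on an intervention rate of about 13%. Taken as loose wording, it costs no power and leaves only a wrong figure in the end-of-study definition. A reader might infer that the trial is planned to be underpowered. The documents do not support that: the sample-size sections plan for 134 consistently, and 134 with 25% attrition delivers the 100 required.

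**What to change.** Amend section 4.9 to agree with the synopsis, section 1.1 and section 2.1:

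- Give 134 randomised (67 per arm) as the recruitment target, and mention 100 (50 per arm) only as the number expected for the primary analysis.
- Define the end of study as the date of the last randomised participant's final follow-up, meaning T5 at 12 months after surgery or earlier death, withdrawal or loss to follow-up.
- Do not tie the end to a fixed count. A count of 100 recruited contradicts the plan. A requirement that all 134 complete T5 could never be met if recruitment closes short or if patients die or withdraw.

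The cost is a short rewording of one section. It needs no patients beyond the planned 134, no new data and no change to the analysis.

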#### **4.10. Procedures for unblinding (if applicable)**

**Blinding:** Research team members independent to the Prehab team will analyse the data and outcome measurements of participants and will be blinded to participant group assignment.

The cardiothoracic physiotherapists, managing the post-operative care of patients will be blinded to which group the participant has been randomised to (the intervention arm or control arm).

If a patient is readmitted to hospital following discharge home, it will not be necessary to unblind physiotherapists with the patients new hospital admission. This is because the intervention arms will be pre-operative and will not influence the safety of patients post-operative or influence their medical management.

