#### **2.4.3. Project statistician / methods expert**

Statistical analyses will be performed using SPSS statistical software, version 20.0 (IBM Corporation, Armonk, NY, USA) by the chief investigator who is familiar with the use of this software and has previously published data in the lancet journals eclinical medicine (15).

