## 7.3. Safety Endpoints

Safety analysis will include rate of complications and mortality and are categorical data sets. The chi-square test or Fisher's exact test will be used to assess the safety of IMT in combination with Prehab compared with its control i.e., standard Prehab using a significance level of 0.05.

The study may be ended prematurely, if there is a significant increase in post-surgical mortality or complications in the study group.

Additionally, if any of the patients in the intervention group experience syncope symptoms whilst using the device they will be advised to stop and will be withdrawn from the study.

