### **8.4. Data monitoring**

Data will be monitored electronically by the whole of the research team and escalated to the CI accordingly.

The data will be reviewed by the CI and PI in a monthly meeting.

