## 10. Trial Committees

A trial management group (TMG) will provide overall supervision for this study and to take steps to reduce deviations from the protocol to a minimum, periodic review of the trials progress, to review safety data and to help resolve any differences within the research team or between the team and trial sponsor. The TMG operates on behalf of the Trial Sponsor and is to ensure that the trial is conducted according to the UK Research Governance Frameworks for Health and Social Care, the principles of Good Clinical Practice (GCP) and all relevant regulation and local policies. The TMG will also ensure the trial runs to time and budget as much as feasible.

The TMG will consist of the chief investigator, principle investigator, study staff and representatives from the sponsor.

The frequency of the TMG will be meet monthly and then quarterly and can be subject to change as the study progresses. An agenda will be sent before each meeting. Minutes of each meeting will be taken, and circulated to the TMG members for accuracy.

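### Section 4.10 promises analysis by blinded, independent team members, but 2.4.3 gives the analysis to the chief investigator, whose blinding is nowhere stated; blinded PPC grading is also not secured

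*Protocol*

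**What the plan says.** **Who analyses.** Section 4.10, on blinding, states: "Research team members independent to the Prehab team will analyse the data and outcome measurements of participants and will be blinded to participant group assignment". Section 2.4.3, on the project statistician, says that the SPSS analyses are performed "by the chief investigator who is familiar with the use of this software" and does not mention blinding. The Communication Plan in Appendix 2 also puts data management and analysis under the chief investigator's oversight.

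**What else the chief investigator does.**
- Section 4.6: outcome measures are assessed by telephone, in the physiotherapy department, "or the satellite center by the CI or research team".
- Section 6.1.1: the Chief/Principal Investigator is described as responsible for the patient's care and judges whether an event is serious.
- Section 8.4: "The data will be reviewed by the CI and PI in a monthly meeting".
- Section 10: the trial management group reviews safety data, and "The TMG will consist of the chief investigator, principle investigator, study staff and representatives from the sponsor".
- Section 7.3: the trial may stop early "if there is a significant increase in post-surgical mortality or complications in the study group".

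**Who records PPC.** The data collection text under 2.4.1 gives PPC and length of stay after surgery to the researcher and calls this normal practice of the prehab service. The table in 4.5 also lists the researcher. Section 8.1 has the principal investigator and research team write outcomes on paper that forms part of the physiotherapy notes. Section 4.1 places written records of research events, with randomisation as an example, in the physiotherapy notes too. Besides the analysing members, 4.10 declares one other group blinded: the physiotherapists who manage post-operative care.

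**The concern.** The protocol assigns one task, the analysis, in two ways. One assignment carries two safeguards (blinding and independence from the Prehab team). The other names a person for whom neither safeguard is stated. A later analysis plan would have to depart from one of the two sections, so this is not a detail that a protocol can simply leave open.

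Participants know whether they trained with the device, so protection against bias has to come from the people who record, grade and analyse. The primary outcome is a PPC graded by Clavien Dindo, and recording and grading it calls for judgement. If the grader or the analyst knows the arm, that protection is lost and cannot be restored after the data have been seen.

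**Working it through.** **Step 1. Can 4.10 and 2.4.3 both be followed?** Section 4.10 requires the analyst to be (a) independent of the Prehab team and (b) blinded to group. Section 2.4.3 makes the chief investigator the analyst. Both hold only if the chief investigator meets (a) and (b).

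| Source | Bearing on (a) or (b) |
|---|---|
| 2.4.3, Appendix 2 | Analyst and overseer of the analysis; neither (a) nor (b) mentioned |
| 4.6 | May assess outcomes, as an alternative to the research team |
| 6.1.1 | Patient care and judgement of seriousness |
| 8.4 | Sees accruing data monthly; not said to be by arm |
| 10 with 7.3 | Sits on the group that reviews safety data; the stopping criterion concerns one arm, but the text does not say who makes that comparison |
| 4.10 | Blinds the independent analysing members and the post-operative physiotherapists; the chief investigator is not named |

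No row establishes (a) or (b). Several make (b) doubtful. None shows outright that it fails.

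**Step 2. Is blinded PPC grading secured?** Section 4.10 speaks of outcome measurements as well as data, so it appears to intend blinded assessment. The collection sections do not carry this through:
- no section names who assigns the Clavien Dindo grade;
- 2.4.1 ties PPC collection to prehab service practice;
- 8.1 and 4.1 together put outcome sheets and the record of randomisation in the same notes.

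That the arm itself is written there, and that the PPC collector knows it, are inferences.

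**Step 3. Scale, as an illustration only.** The plan has no figure of its own to reproduce on this point. Inputs from 2.4.1: PPC rate 36.7%, two-sided level 0.05, 50 analysed per arm. Assumptions: no true effect, and a share u of IMT-arm PPCs goes unrecorded while control events are complete. The protocol gives no value for u, so a range is shown.

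Control events X ~ Bin(50, 0.367). Recorded IMT events Y ~ Bin(50, 0.367 × (1 − u)). The uncorrected statistic is

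χ² = 100 × [X(50 − Y) − (50 − X)Y]² / [(X + Y)(100 − X − Y) × 50 × 50],

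significant above 3.841. Summing the exact probabilities over all (X, Y):

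| u (assumed) | Mean events missed, 50 × 0.367 × u | Recorded IMT rate | P(significant, favouring IMT) | P(significant, either way) |
|---|---|---|---|---|
| 0% | 0 | 36.7% | 2.5% | 5.0% |
| 5% | 0.9 | 34.9% | 3.8% | 5.4% |
| 10% | 1.8 | 33.0% | 5.7% | 6.6% |
| 20% | 3.7 | 29.4% | 11.7% | 12.0% |
| 30% | 5.5 | 25.7% | 21.8% | 21.9% |

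For a single result: 18 v 10 events gives χ² = 100 × (18 × 40 − 32 × 10)² / (28 × 72 × 2500) = 3.17, p = 0.075. With 18 v 9, χ² = 100 × (18 × 41 − 32 × 9)² / (27 × 73 × 2500) = 4.11, p = 0.043. An exactly equal 18 v 18 would therefore need nine missed IMT-arm events to become significant. Small losses matter mainly for results already near the threshold.

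**The case against.** The best defence is that 4.10 sets the conditions (blinded, independent) and 2.4.3 only says who runs the software, so a chief investigator outside the Prehab team and kept blind would satisfy both. That reading is possible, but it needs two facts that the protocol never states.

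Other objections stand and limit the point:
- A reader might infer that the analysis will be unblinded. The text does not go that far: the monthly review is not said to be by arm, and 7.3 does not say who compares the arms.
- Section 4.6 opens with a quality-of-life questionnaire that participants complete, and names the chief investigator only as an alternative to the research team. It does not show the chief investigator assessing PPC.
- A reader might infer from 2.4.3 and 4.4 that the chief investigator belongs to the Prehab team, because the standard programme comes from a study that the chief investigator published. Authorship does not show who delivers Prehab in this trial.
- A reader might infer that PPC collectors know the arm. Section 4.1 says that randomisation is recorded, not that the arm is.
- A reader might measure the harm by an analyst's freedom to choose between any PPC and grade 2 or above, since 1.1 mentions both. That is a separate ambiguity, cured by fixing the endpoint whoever analyses.
- Not naming a PPC grader is a gap that a working document could fill. It is therefore secondary here and rests on the shared notes and the link to the prehab service.
- The under-recording shares have no source in the protocol.

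**Conclusion.** The concern holds as an internal inconsistency that should be fixed. Sections 4.10 and 2.4.3 name different analysts, the chief investigator is nowhere said to be blinded or independent of the Prehab team, and that person's other roles make blinding doubtful without disproving it. This conclusion rests on the text alone and needs no assumption about by-arm review.

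The secondary point holds with moderate confidence: blinded PPC grading appears intended but is not secured.

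The size cannot be derived from the protocol. If 10% to 20% of IMT-arm PPCs went unrecorded (about two to four events), the chance of a false result favouring IMT would be 5.7% to 11.7% instead of 2.5%. These figures concern biased PPC recording only. They do not measure the effect of who runs the analysis, and they are not a forecast.

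**What to change.** 1. **Section 2.4.3.** Amend it so that the independent, blinded members described in 4.10 run the primary analysis. Alternatively, let the chief investigator run it on a dataset with coded arms, provided that he or she has seen no by-arm data before that analysis is locked and that others do any safety review by arm. The first option is simpler: it leaves the safety roles in 6.1, 7.3 and section 10 untouched, whereas under the second, assessing individual serious events could still reveal who used the device.
2. **Sections 2.4.1 (data collection) and 8.1.** State that PPC is graded from the medical record by the blinded members of 4.10, or by the blinded post-operative physiotherapists if they are confirmed to have no Prehab role.
3. **Sections 4.1 and 8.1.** Keep the allocation record in a separate file, apart from the notes that the grader uses.

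The cost is a small grading task and one extra file. Section 4.10 describes a role and does not name a person, so the trial must confirm that someone able to run the analysis fills it. Patients undergo no additional procedure.
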